## 3.0 RESEARCH SUBJECT SELECTION

### Eligibility Criteria

#### Inclusion criteria:

- Diagnosis of metastatic colorectal cancer **OR** locally advanced pancreatic cancer **OR** metastatic pancreatic cancer **AND**
  - Is making a decision regarding treatment with 1st or 2nd line palliative chemotherapy. **OR**
  - Is receiving 1st line palliative chemotherapy, and is therefore likely to make a future decision about 2nd line chemotherapy (either for cancer progression or toxicity). This cohort of patients will be eligible for study enrollment and baseline assessment, but will not be subject to randomization until the time of their next treatment decision.
- Treating oncologist has recommended consideration of one or more of the regimens for which we have developed informed consent (IC) toolkits (FOLFOX, FOLFOX + bevacizumab, FOLFIRI, FOLFIRI + bevacizumab, FOLFIRINOX, Gemcitabine, or Gemcitabine + nab-paclitaxel).
  - Patients who are also considering treatment on a clinical trial are eligible, including those considering treatment on a clinical trial of FOLFOX (+/-bev) + investigational agent, or FOLFIRI (+/-bev) + investigational agent
- Age  $\geq$  21
- English proficient

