#### **Instrument 1: Baseline Assessment (See Appendix C)**

The baseline assessment will assess socio-demographics, information/communication preferences, decision control preferences, and illness understanding. Patients will complete this assessment after consenting for the study, but before randomization. The baseline assessment takes approximately 5 minutes to complete.

**Title:** Improving Informed Consent for Palliative Chemotherapy: RCT of Usual IC versus Investigational IC

**Overall PI:** [name], Dana-Farber Cancer Institute

**Dana-Farber protocol version no./date:** v17 / August 30, 2017

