## 5.4 Data Collection

### Summary of measures used at each patient assessment

Domain	Measures	Baseline Assessment	Post-Decision Assessment	Follow-up Assessment
Socio-demographics a	Standard assessments	• x		
Health Literacy and numeracy b	Stagliano  (2013), Lipkus  (2001)	• x		
QOL c	FACT-G 	•	•	•
Optimism d	Life Orientation Test-Revised 	•		
Distress e	Emotional wellbeing component of FACT-G 	•	•	•
Communication & decision preferences f	Control Preferences Scale 	•		
	Preferred information for chemotherapy decision (for study)	• x		
	Prognostic communication preferences, Meropol 	• x		
Illness understanding	Developed for study	• x		
Use of IC booklet and video	Video use monitored via password protected website, booklet use monitored by survey		•	• x
Quality of Informed Consentg				
Core Understanding				
Chemotherapy risks	Modified from Leighl et al 		•	
Chemotherapy benefits	Adapted from CANCORS  (primary outcome)		•	• x
Decision Making				

**Title:** Improving Informed Consent for Palliative Chemotherapy: RCT of Usual IC versus Investigational IC

**Overall PI:** [name], Dana-Farber Cancer Institute

**Dana-Farber protocol version no./date:** v17 / August 30, 2017

Adequate information	Developed for study			
Decisional involvement	Modified Control Preferences Scale 		•	
Decisional conflict	Modified SURE assessment 		•	
Satisfactionh				
MD-patient relationship	Revised Human Connection Scale 		• x	
With study IC tools/ standard IC	Developed for study		•	
With decision	Brehaut decisional regret scale 			•
Doctor-patient communicationi				
Patient-centered communication	Aurora and Mazor 		•	• x
Prognostic communication	Developed for study			• x
Prognostic Understanding j	Adapted from CANCORS 			• x
Advance Care Planning	Chart abstraction (DNR) and patient report (healthcare proxy)			• x

• Patient Participant Assessment

x Caregiver Participant Assessment

**Clinical characteristics:** Date of diagnosis (or metastatic recurrence), location of metastases, prior adjuvant chemotherapy, and ECOG performance status via chart review.

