**aSocio-demographics:** Age, race/ethnicity, marital status, education, insurance status, preferred language, religious affiliation via chart review; and a one-item measure of religious coping via participant questionnaire.

**bHealth Literacy & Numeracy:** Participants will complete a validated 1-item screening measure for health literacy developed by Stagliano, and a validated 1-item screening measure to assess numeracy.

**cQOL:** QOL will be assessed by the well validated Functional Assessment of Cancer Therapy-General (FACT-G), a 27-item scale assessing physical wellbeing, social/family wellbeing, functional wellbeing, emotional wellbeing, and functional wellbeing.

**dOptimism:** The validated 7-item Life Orientation Test-Revised will assess trait optimism at baseline.

**eDistress:** will be measured using the emotional wellbeing subscale of the FACT-G QOL survey.

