## 5.5 Description of Study Process

1. **IDENTIFY PARTICIPANTS:** The research assistant will identify potentially eligible participants by looking through new patient and existing patient scheduling reports, as well as by accepting physician referrals. We are requesting a HIPAA waiver of authorization so that the research assistant may look in the Electronic Health Record to determine eligibility before approaching potentially eligible participants.
2. **CONSENT PARTICIPANTS:** The research assistant will approach the eligible participant either in-person or over the phone and introduce the study, answer any questions, and offer the potential participant time to think it over. If/When the potential participant decides to participate, the research assistant will obtain signed informed consent for participation in the research study. If the potential participant decides NOT to participate, the study team will not contact the person again. The caregiver will also be invited to participate; they will be given a study letter that contains the elements of informed consent.
3. **ADMINISTER BASELINE ASSESSMENT:** If the participant consents, the research assistant will administer the baseline assessment. For patients who are unable to complete the baseline assessment immediately following study consent (for example, if they are too fatigued or emotionally overwhelmed after their oncology consultation) the protocol will allow for participants to be randomized (see 4.0) and then complete the baseline survey (within two weeks of randomization). Questionnaire-based instruments will be administered 1) in person by a trained research assistant at the time of a routinely scheduled visit, 2) by e-survey, 3) by phone, 4) or by postal mail. Mode of collection will be recorded. The baseline assessment takes approximately 5 minutes to complete.
4. **RANDOMIZE PARTICIPANTS:** The research assistant will contact the central research assistant at Dana-Farber to randomize the participant:
  - A. For patients making a chemotherapy treatment decision at the time of study enrollment: After study consent and the baseline assessment, the study team will then randomize the patient to either the Usual IC Arm or the Investigational IC Arm of the study.

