## 5.6 Adverse Reaction and Their Management

Reporting adverse or unanticipated events: Investigators do not anticipate needing to remove a subject from the study for any adverse events. Subjects may decline to participate or withdraw their consent, as per standard policies and procedures. If a circumstance arose where the investigators were concerned about a subject's safety as a result of the study, the subject would be removed from the study. The proposed research will comply with the regulations set forth in CFR Part 46, Protection of Human Subjects. All staff involved in the proposed protocol have been educated regarding HIPAA regulations and fully understand their responsibility to safeguard the personal health information of every participant involved in the research.

Anticipated reactions: Adverse reactions are expected to be minimal. A possible adverse reaction as a result of participating in this study is psychological distress as a result of viewing the informed consent (IC) video and booklet, which discuss the fact that chemotherapy does not cure metastatic colorectal cancer. The IC booklet also includes an optional section that discusses typical life expectancy with and without chemotherapy. This optional section is sealed, and is preceded by a cautionary sign with explanation that normalizes patients' decision of whether or not to review it. The video similarly includes an optional web-link to a segment discussing life expectancy. This optional video web-link is also preceded by a cautionary explanation that normalizes patients' decision of whether or not to view this segment. Participants may also find some survey items regarding their prognostic understanding to be distressing; however we have worded these items carefully and with the input of patient stakeholders to ensure their sensitivity and acceptability to patients.

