*Hypothesis:* Patients randomized to the intervention will be more likely to discuss their end-of-life care preferences with their healthcare proxy, and with their oncologist as compared to patients randomized to the usual IC process.

We will adhere to standard reporting principles delineated by the CONSORT statement for conduct and reporting of randomized trials. Primary reports will reflect the as randomized, "intention to treat" principle, however, we will also describe results according to actual exposure to the study interventions (based on patients' self-report of whether they reviewed the standard-of-care, or investigational chemotherapy informed consent materials). Fisher's exact test will test the difference between the study arms in the first primary outcome (the proportion of patients at follow-up assessment who fail to understand that chemotherapy is "not at all likely" to cure their cancer, as assessed by an item from CANCORS). We will also test the influence of the intervention on secondary outcomes (e.g. understanding of the goal of palliative chemotherapy, chemotherapy risks, decisional conflict,

**Title:** Improving Informed Consent for Palliative Chemotherapy: RCT of Usual IC versus Investigational IC

**Overall PI:** [name], Dana-Farber Cancer Institute

**Dana-Farber protocol version no./date:** v17 / August 30, 2017

achievement of preferred role in decision-making, satisfaction with chemotherapy IC process, prognostic understanding, advance care planning, discussion of end-of-life care preferences, satisfaction with MD communication, satisfaction with informed consent (IC) documents, decisional regret, emotional distress) using Fisher's exact or chi-square tests for dichotomous outcomes, and t-tests or Wilcoxon tests for linear outcomes. For missing data for primary or secondary outcomes, we will employ multiple imputation under a missing at random assumption.

Subset analyses will explore the effect of the intervention on 1) patients making a decision about 1st line treatment, 2) patients making a decision about 2nd line treatment, 3) patients with colorectal cancer, and 4) patients with pancreatic cancer.

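### Emotional distress is compared between arms with no baseline covariate, although the same FACT-G subscale is scheduled at baseline: the test is valid but needlessly imprecise

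*Combined protocol and SAP*

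**What the plan says.** Section 6.0 gives twelve examples of secondary outcomes, the last being distress: "decisional regret, emotional distress) using Fisher's exact or chi-square tests for dichotomous outcomes", followed by "and t-tests or Wilcoxon tests for linear outcomes". It names no covariate. It does not say whether the score or its change from baseline is compared, or at which assessment.

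The measures table in Section 5.4 gives the distress instrument as "Emotional wellbeing component of FACT-G" and marks it at baseline, post-decision and follow-up. The note to the table confirms that distress "will be measured using the emotional wellbeing subscale of the FACT-G QOL survey". Section 5.6 states: "A possible adverse reaction as a result of participating in this study is psychological distress".

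Three further places bear on the baseline score:

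- Section 5.2 describes the baseline content without quality of life or distress: "The baseline assessment will assess socio-demographics, information/communication preferences, decision control preferences, and illness understanding". Section 5.7 repeats that list.
- Section 5.5, step 3, lets patients who cannot complete the baseline survey straight after consent be "randomized (see 4.0) and then complete the baseline survey (within two weeks of randomization".
- Under Section 3.0, patients already on first-line treatment "will be eligible for study enrollment and baseline assessment, but will not be subject to randomization until the time of their next treatment decision".

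The only regressions planned for distress are the exploratory moderator models in Section 6.0. The adjustment factors given there as examples are age, race/ethnicity and marital status.

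**The concern.** A patient's distress before randomization usually says something about distress two or three months later. A two-sample test of the follow-up score leaves that variation in the error term. A linear model that includes the baseline score removes it and also accounts for chance imbalance in baseline distress between the arms.

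This matters more for distress than for most secondary outcomes. Distress is the harm the protocol foresees from the tools, and Section 6.0 itself hypothesizes that it may rise in patients who prefer a vague, supportive style of prognostic communication. The sample size was set for the cure item, and no precision is stated for distress. The width of the confidence interval therefore decides how much the trial can say about this harm, and the plan makes it wider than the scheduled data require.

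**Working it through.** **Inputs from the documents.** Section 6.0 (Power): 60% inaccurate expectations, 20 points absolute decrease, 80% power, one-sided 2.5%, 194 patients. Section 4.0: 1:1 allocation, so 97 per arm. Section 5.1: 244 patients, so 122 per arm at most.

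**Assumed.** The documents give neither the SD of the subscale nor the correlation r between baseline and later scores. Results are therefore in SD units, with r from 0.3 to 0.7. The low end is included because in the deferred cohort the baseline may precede randomization by a long time, which would weaken r.

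**Step 1: the plan's own figure.** For 60% versus 40%, without continuity correction:

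n per arm = [1.960 × √(2 × 0.5 × 0.5) + 0.842 × √(0.6 × 0.4 + 0.4 × 0.6)]² / 0.20² = (1.386 + 0.583)² / 0.04 ≈ 96.9, rounded up to 97.

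The total is 194, as stated. This concerns the primary outcome only.

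**Step 2: distress as planned.** At two-sided 5% and 80% power, a t-test of the score can detect (1.960 + 0.842) × √(2/n) SD:

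- 97 per arm: 2.802 × 0.1436 = 0.402 SD. The 95% CI half-width is 1.960 × 0.1436 = 0.281 SD. Power for a 0.3 SD difference is 55%.
- 122 per arm: 2.802 × 0.1280 = 0.359 SD.

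**Step 3: with baseline adjustment.** The residual SD is the SD times √(1 − r²), so each figure is multiplied by that factor.

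| r | √(1 − r²) | SE reduction | Detectable, 97 per arm | CI half-width, 97 per arm | Power for 0.3 SD, 97 per arm | Detectable, 122 per arm |
|---|---|---|---|---|---|---|
| none | 1 | none | 0.402 SD | 0.281 SD | 55% | 0.359 SD |
| 0.3 | 0.954 | 4.6% | 0.384 SD | 0.268 SD | 59% | 0.342 SD |
| 0.5 | 0.866 | 13.4% | 0.348 SD | 0.244 SD | 67.5% | 0.311 SD |
| 0.7 | 0.714 | 28.6% | 0.287 SD | 0.201 SD | 83% | 0.256 SD |

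At r = 0.5, 194 patients carry the information of 194 / 0.75 ≈ 259 unadjusted patients.

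**Step 4: if a change score is meant.** With equal SDs at both times, the SD of the change is the SD times √(2(1 − r)). At 97 per arm the detectable difference is 0.476 SD at r = 0.3, 0.402 SD at r = 0.5 and 0.312 SD at r = 0.7. The adjusted model does better each time (0.384, 0.348 and 0.287 SD), so the point stands under either reading of Section 6.0.

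**Limits.** Steps 3 and 4 assume that every analysed patient has a score from before randomization; each patient without one reduces the gain. The 122 per arm is an upper bound, because Section 4.0 says that patients who reach no new treatment decision during the study will not be randomized.

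**The case against.** The strongest case against the point has four parts.

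**The plan contains no error.** A reader might infer that the unadjusted comparison is biased. It is not: randomization makes it valid. Distress is also one of twelve listed secondary outcomes, with no power claim attached. This stands, and it limits the point to precision.

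**The plan does not say that the baseline is ignored.** Section 6.0 leaves open whether a score or a change is tested, and the moderator models list their covariates only by example. It would go too far to say that the follow-up score alone will be compared. But a change score is less precise than the adjusted model throughout the range shown, and exploratory moderator models are not the comparison of arms.

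**The baseline is imperfect.** Section 5.5 lets it be completed up to two weeks after randomization, in an unblinded trial whose tools are to be given as soon as possible. The examples it gives are patients too tired or too upset to answer, which bears directly on distress. Adjusting for a score that the intervention may have changed could mask harm. This stands, and it changes the remedy. In addition, Sections 5.2 and 5.7 leave quality of life and distress out of the baseline assessment, and Section 5.2 puts it at about 5 minutes although Section 5.4 gives the FACT-G 27 items. Whether the score is collected at baseline must therefore be settled.

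**The consequence is speculative.** A reader might infer that a non-significant result will be reported as showing no harm, and that a non-inferiority margin is needed. No section plans such a reading. A margin is a separate and debatable proposal, and the point does not depend on it.

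**Conclusion.** The point holds as a loss of precision in the comparison for the one harm the protocol names. No section plans a comparison of arms on distress adjusted for baseline, although the measures table schedules the necessary score.

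The size depends on a correlation that the documents do not supply. It is small at r = 0.3, about 5% of the standard error, and material at 0.5 to 0.7, about 13% to 29%. A reader might quote only the upper part of that range. The documents do not support doing so, since part of the cohort may have a baseline taken long before randomization.

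The conclusion assumes that the table in Section 5.4 is right about the baseline content and that most patients complete the survey before randomization.

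**What to change.** In Section 6.0, replace the t-test or Wilcoxon test for FACT-G emotional wellbeing by a linear model at post-decision and at follow-up. The terms are arm, baseline score taken before randomization, and line of therapy (the randomization stratum). Report the adjusted difference with its 95% CI. Treat the FACT-G total, which is on the same schedule, in the same way.

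Add a rule for the covariate. Only scores completed before randomization are used. A score completed afterwards counts as a missing covariate and is handled by a method blind to arm, such as mean imputation with a missingness indicator. The patient stays in the analysis.

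Reconcile the baseline descriptions in Sections 5.2 and 5.7 with the table in Section 5.4.

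The cost is a few sentences. No new patients or measurements are needed if the baseline form carries the FACT-G as the table shows. If it does not, the gain is not available from the data as collected, and the table should be corrected.

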## 1.0 INTRODUCTION

### 1.1 Overview

Patients are routinely asked to sign an informed consent document prior to starting chemotherapy, indicating they understand the risks and benefits of treatment. Although this could be a strategic moment to equip patients with information they need to make truly informed medical decisions, many patients and caregivers note that these conversations are less useful than they could be. The informed consent process and its associated documents suffer several limitations: 1) risks are emphasized over benefits; 2) educational materials focus on individual drugs instead of regimens; 3) information is presented in written instead of alternative written/audiovisual format; and 4) the patient perspective is lacking.

Our research team, consisting of oncologists, nurses, and cancer patients has worked together to create a suite of informed consent tools which better convey the risks and benefits of common palliative chemotherapy options for advanced GI cancer. Each informed consent tool consists of a video and written booklet, and improves upon existing resources in several ways: 1) balanced discussion of benefits as well as risks, 2) focus on regimens rather than drugs, 3) use of both written and video format, and 4) inclusion of the patient perspective (e.g. video clips of patients describing their experience).

The overarching objective of this project is to conduct a randomized clinical trial to demonstrate if the informed consent toolkit the study team has developed improves the quality of informed consent for palliative chemotherapy. If effective, the tools will be amenable to broad dissemination via patient accessible cancer education websites and oncology clinics.

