## 5.0 STUDY DESIGN AND METHODS

### 5.1 Design/Study Type

Non-treatment intervention, randomized clinical trial of up to 350 participants [244 patient participants plus up to 106 of their caregivers as caregiver participants] (social behavioral research).

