## 6.0 STATISTICAL ANALYSIS

We will test hypotheses that the study intervention---informed consent (IC) video/written tools developed with patient and clinician input---can improve patient-centered decision making for subjects contemplating palliative chemotherapy for advanced GI cancer.

**Objective 1:** Determine if the multi-media informed consent (IC) tools improve patients' understanding of benefits and risks of palliative chemotherapy as compared to the standard IC process.

*Hypothesis:* The multi-media IC tools will decrease the likelihood that patients overestimate the curative potential of palliative chemotherapy as compared to the usual IC process. (primary study outcome)

*Hypothesis:* The multi-media IC tools will increase the likelihood that patients understand the goal of treatment as compared to the usual IC process.

*Hypothesis:* The multi-media IC tools will increase the likelihood that patients will have an accurate understanding of the risks of chemotherapy as compared to the usual IC process.

**Objective 2:** Determine if the multi-media informed consent (IC) tools decrease decisional conflict, increase the likelihood patients achieve their preferred role in decision-making, and increase satisfaction with the chemotherapy IC process as compared with the standard IC process.

*Hypothesis:* The multi-media IC tools will decrease decisional conflict as compared to the usual IC process

*Hypothesis:* The multi-media IC tools will increase the likelihood that patients achieve their preferred role in treatment decision-making as compared to the usual IC process

*Hypothesis:* The multi-media IC tools will increase satisfaction with the chemotherapy IC process as compared to the usual IC process

**Objective 3:** Determine if the multi-media informed consent (IC) tools enhance patients' prognostic understanding, increase advance care planning, and facilitate patient-physician conversations about end-of-life care preferences.

*Hypothesis:* Patients randomized to the intervention will have more realistic expectations of their prognosis as compared to patients randomized to the usual IC process.

*Hypothesis:* Patients randomized to intervention will be more likely to have designated a healthcare proxy and more likely to have a DNR order as compared to patients randomized to the usual IC process

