Because the effects of our intervention may be moderated by patient characteristics (e.g. age, race/ethnicity, health literacy and numeracy, communication preferences, decisional control preferences), we plan to conduct exploratory analyses investigating whether these factors moderate the effect of the intervention on outcomes including 1) accurate understanding of chemotherapy benefits, 2) satisfaction with communication and the IC tools, 3) decisional involvement, or 4) emotional distress. For example: we hypothesize that the IC tool may lead to decreased distress among patients who prefer a detail-oriented prognostic communication style, whereas it may lead to increased distress among patients who prefer a vague and support-focused prognostic communication style. We would also hypothesize that the effects of

**Title:** Improving Informed Consent for Palliative Chemotherapy: RCT of Usual IC versus Investigational IC

**Overall PI:** [name], Dana-Farber Cancer Institute

**Dana-Farber protocol version no./date:** v17 / August 30, 2017

the intervention may be greater among patients with higher health literacy scores. We will test these hypotheses using multivariable logistic or linear regression analyses (depending upon the dependent variable), including interaction terms for collinear factors, and controlling for potential confounding factors (e.g. age, race/ethnicity, marital status).

**Power:** In the CANCORS study, 80% of mCRC patients on 1st line chemotherapy thought that chemotherapy could potentially cure their disease (median of 4 months post-diagnosis). Based on previous series and projections about our patient mix, we anticipate that 60% of patients will have inaccurate expectations about the benefits of chemotherapy. If the intervention strategy is able to better align expectations with likely outcomes by one third (33%) we will deem the intervention as having major impact. If this benchmark 33% reduction is not achieved but the intervention exposed subjects nonetheless have expectations that are more accurate, we will view the intervention as beneficial but lacking major impact. Assuming a baseline 60% rate of inaccurate expectations about the benefits of chemotherapy, with a total of 194 patients, we will have 80% power to detect a 33% decrease (20% absolute decrease) in inaccurate expectations among patients exposed to the intervention with a one-sided type I error of 2.5%.

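### The 'beneficial' conclusion is not tied to the primary test: read literally, a tool with no effect would earn it about 47% of the time, against 1.7% if significance is required

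*Combined protocol and SAP*

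**What the plan says.** Section 6.0 (Power) defines two favourable conclusions. The upper tier applies if the strategy manages to "better align expectations with likely outcomes by one third (33%) we will deem the intervention as having major impact". The lower tier applies if that benchmark is missed but "the intervention exposed subjects nonetheless have expectations that are more accurate, we will view the intervention as beneficial but lacking major impact".

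The inferential machinery stands elsewhere in Section 6.0. The section opens with "We will test hypotheses that the study intervention" can improve decision making, and later states that "Fisher's exact test will test the difference between the study arms in the first primary outcome", namely the proportion with inaccurate expectations at the follow-up assessment. The one-sided 2.5% error rate appears in the sample-size sentence, which assumes 60% inaccurate under usual consent, 194 patients and 80% power for a 20-point absolute drop.

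No sentence makes either label depend on the test or its error rate.

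**The concern.** The lower tier is a stated conclusion, and its only condition is that expectations be more accurate. Taken at its word, any observed advantage qualifies, however small. The same data could then be reported as 'beneficial' or as 'benefit not shown', depending on a reading that the plan leaves open.

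The label may matter beyond the report. Section 1.1 says: "If effective, the tools will be amenable to broad dissemination via patient accessible cancer education websites and oncology clinics". The documents give no separate definition of effective. Assignment is unblinded, so the reading should be fixed before anyone sees outcome data.

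The wording is also loose about which comparison it means. It speaks of subjects exposed to the intervention, while Section 6.0 describes both an as-randomized analysis and one by self-reported exposure.

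**Working it through.** **Inputs.** From Section 6.0 (Power): control rate 60% inaccurate, intervention rate 40% under the design effect, one-sided alpha 2.5%, 194 patients. With 1:1 allocation (Section 4.0) that is 97 per arm. Section 5.1 plans "244 patient participants plus up to 106 of their caregivers as caregiver participants"; 122 per arm is therefore an upper bound, reached only if all 244 patients are randomized and assessed.

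**The plan's own figure.** The pooled normal-approximation formula without continuity correction is

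n = [z(0.975)·√(2·p̄(1−p̄)) + z(0.80)·√(p1(1−p1) + p2(1−p2))]² / (p1−p2)²

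With p1 = 0.60, p2 = 0.40 and p̄ = 0.50:

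n = [1.960·0.7071 + 0.8416·0.6928]² / 0.04 = 96.9, so 97 per arm and 194 in total.

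The stated sample size is reproduced.

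**Single tables (one-sided Fisher p), with 58/97 inaccurate under usual consent.**

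| Intervention arm | Difference | p | More accurate? | Significant at 2.5%? |
|---|---|---|---|---|
| 57/97 | 1.0 point | 0.50 | yes | no |
| 44/97 | 14.4 points | 0.031 | yes | no |
| 43/97 | 15.5 points | 0.022 | yes | yes |

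The literal rule needs one patient fewer; the test needs fifteen fewer.

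**Operating characteristics.** Let X and Y be the inaccurate counts in the usual and intervention arms, independent binomials with n per arm. Summing exactly over all (X, Y):

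- ahead: Y < X
- significant: Y < X and one-sided Fisher p ≤ 0.025
- disputed: ahead but not significant

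| True rates | Ahead, 97/arm | Significant | Disputed | Ahead, 122/arm | Significant | Disputed |
|---|---|---|---|---|---|---|
| 60% vs 60% | 47.1% | 1.7% | 45.4% | 47.4% | 1.9% | 45.5% |
| 60% vs 55% | 73.7% | 8.0% | 65.6% | 76.6% | 9.4% | 67.2% |
| 60% vs 50% | 90.9% | 24.4% | 66.5% | 93.5% | 29.3% | 64.1% |
| 60% vs 45% | 97.9% | 50.4% | 47.5% | 98.9% | 59.4% | 39.5% |
| 60% vs 40% | 99.7% | 76.4% | 23.3% | 99.9% | 84.9% | 15.0% |

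**Check on the null row.** By symmetry P(ahead) = (1 − P(tie))/2. At 97 per arm P(tie) = 5.84%, giving (1 − 0.0584)/2 = 47.1%. At 122 per arm P(tie) = 5.21%, giving 47.4%. At 97 per arm the figure stays between 46% and 47% for common rates from 40% to 80%, with 1.6% to 1.9% significant.

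**Lower tier alone.** Leaving out results that reach the one-third benchmark (0.05% under no effect at 97 per arm) moves the 47.1% only to 47.0%.

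**Where the reading matters most.** Between 5 and 10 points the disputed share peaks at 69.0% (7.75 points, 97 per arm) and 69.4% (7.0 points, 122 per arm). Significance becomes the likelier result from about 14.75 points at 97 per arm and 13.5 points at 122.

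**Upper tier.** At a 60% control rate, an observed reduction of one third or more without significance has probability of at most 0.000003 at 97 per arm. The gap therefore concerns the lower tier.

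**The case against.** The best reply is that significance is implied. The labels sit in the Power paragraph, where their job is to justify one third as the effect worth detecting, and the upper tier is phrased in terms of what the strategy is able to do. The section speaks of testing hypotheses, names Fisher's test, and gives the error rate two sentences later. On that view the lower tier means shown to be more accurate, but by less than a third. This is a fair reading and may be the intended one. It is still not written, and the alternative is the plain sense of the words.

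It can also be said that 47% is just the chance of being ahead when nothing is happening, and that 66% to 69% is ordinary low power below the design effect. Both are true. They describe what the unwritten condition governs, not a fault in the test.

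The link to dissemination is an inference: Section 1.1 says effective, not beneficial, and no passage makes a next step depend on the label. The plan also commits to CONSORT and as-randomized primary reporting, so the Fisher result would presumably appear beside any label.

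Finally, confining the point to the lower tier depends on the 60% control rate. At 40%, 39/97 against 26/97 is exactly a one-third reduction with p = 0.034. With true rates of 40% and 26.7% at 97 per arm, a benchmark result without significance occurs about 7% of the time. That is correct, and the fix below covers it.

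**Conclusion.** The concern holds and should be fixed. As written, the plan states a conclusion of benefit whose only condition is direction. With no true effect, that conclusion is reached in 47.1% of trials on the literal reading and 1.7% if Fisher significance is required (97 per arm; 47.4% and 1.9% at 122). The 45.4% in between turns on an unstated choice. For modest true effects of 5 to 10 points, the disputed outcome is the most likely one.

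The figures assume equal arms, complete outcome data, the as-randomized comparison and the plan's 60% control rate; the null figures hardly depend on that rate. They do not claim that the sponsor would apply the literal rule, only that the text permits it. The primary test keeps its error rate, which is why this is a matter of the stated conclusion and not of the analysis itself.

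**What to change.** Add to Section 6.0: 'The intervention will be described as beneficial only if the as-randomized primary Fisher test is significant at one-sided 2.5% in its favour; the 33% benchmark then grades the size of the effect. If the test is not significant, benefit is not established, whatever the direction of the estimate.'

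This puts significance first for both tiers, so it also covers a lower control rate, and it settles that the label refers to the randomized comparison and not to self-reported exposure. It costs two sentences, with no change to design, sample size, test or data collection. The one downside is that a favourable but non-significant result loses its favourable label. If significance was always intended, nothing is lost.
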